5.1.4 Exploratory End points

- To study other exploratory biological and clinical effects of the DIALIVE in patients with ACLF compared with the Standard of Care group. Some of these parameters are centre-specific in line with local expertise, research interest and the capacity to perform these tests. Liver: Changes in MELD score, plasma/serum cCK18/M30 and flCK18/M65 (markers of liver cell death).
- Kidney: Changes in serum creatinine and urinary NGAL (marker of kidney injury).
- Brain: West Haven Criteria to assess changes in severity of hepatic encephalopathy.
- Immune function: Incidence of Infection, changes in white cell count, CRP and assessment of neutrophil and monocyte function.
- Assessment of Coagulation and haemostasis: Incidence of thrombotic or bleeding complications, assessment of proand anti-coagulant clotting factors and complement activation.

Clinical Investigation Plan	CIP YAQ-002	Version: 7.0 10 October 2019
-----------------------------	-------------	------------------------------

5.1.5. Methods and timing for assessing, recording, and analysing variables

All data will be recorded real-time in the subject source documents and entered into an electronic Case Report Form (eCRF) by the investigator and/or his/her delegates within a reasonable period following the study visit. The Sponsor/appointed DM centre will manage and maintain the study database throughout the Investigation. At the conclusion of the Investigation, the database will then be locked and analysed. A final copy of the database will be provided to the study site. Where data is transferred electronically, this will be in accordance with EU data protection Directive (Directive 95/46/EC) and applicable national legislation requirements. There will be a documented record of data transfer and measures in place for the recovery of original information after transfer.

Statistics: A qualified statistician will conduct data analyses, and this will be done independently of data entry. Given the small sample size in this safety study, analyses will be primarily descriptive in nature and will include analyses of both the primary and secondary outcomes and hypothesis. All treated subjects entered into the study will be included in the analyses. A sensitivity analysis will be conducted including all evaluable patients. All serious adverse events will be reported in full detail. Please refer to the Statistical Analysis Plan (SAP) for further details.

5.1.6. Equipment to be used for assessing the clinical investigation

All equipment except for the DIALIVE device, the EAA luminometer for endotoxin analysis, and the Primsmaflex platform¹¹ will be the property of the Investigator(s) and/or institutions and maintained and calibrated according to institutional guidelines. Records of maintenance and calibration will be made available at the Sponsor's request.

5.1.7. Replacement of subjects.

30 evaluable patients will be recruited across all sites to receive either treatment using the DIALIVE or SOC. Screen failures will be replaced to achieve an even balance in each cohort. The patient numbers will be increased and replaced if there are dropouts during the treatment period to allow 30 evaluable patients to be included. Dropouts can be i) patients who withdraw their consent, ii) patients who are considered 'not evaluable' because of an incomplete dialysis cycle (for DIALIVE patients) or iii) if a patient dies in the 10-day period following randomization to the SOC-arm, or iv) patients who are excluded based on a stopping rule.

A dropout rate of 17% is anticipated on the basis of observations made during execution of this study in the first 2 cohorts of patients. Patients who drop-out for reasons of an incomplete dialysis cycle are followed up for a duration of 28 days post-randomization.

5.2. Investigational device exposure

For the randomization an Interactive Wireless Randomization System (IWRS) is used, which is linked to the study data base. Randomization is automatically assigned through the IWRS system. Patients are randomised to either the DIALIVE or SOC arm in a 1:1 ratio.

¹¹ The prismaflex platform will be provided by Yaqrit to those sites that do not have access to such haemofiltration machines. The machine will remain the property of Yaqrit Ltd during and after the study. A mainenance agreement in such circumstances will be established with each institution.

Patients will be assigned into five (5) Cohorts. Each cohort will consist of six (6) patients (3 DIALIVE: 3 SOC). If there are dropouts in any of the following cohorts during the study period, patients will be replaced in each of the cohorts described below to reach the appropriate number of 6 evaluable patients in each cohort.

Cohort 1: including 3 control and 3 DIALIVE treated patients. Cohort 2: including 3 control and 3 DIALIVE treated patients. Cohort 3: including 3 control and 3 DIALIVE treated patients. Cohort 4: including 3 control and 3 DIALIVE treated patients. Cohort 5: including 3 control and 3 DIALIVE treated patients.

5.3. Subjects

5.3.1. Inclusion criteria

- Male or female subjects aged ≥18 years ≤81yr
- Subject is able to provide informed consent to participate in the study, otherwise written informed consent must be
 obtained on behalf of the subject by next of kin or a legal representative in accordance with local ethical and legal
 requirements.
- History indicative of alcohol-related cirrhosis based on clinical, radiological and/or histological evidence.
- History of an acute decompensation event (including but not limited to ascites, gastrointestinal bleeding, hepatic encephalopathy and/or acute bacterial infections), occurring within ≤6 weeks of screening.
- Subject with :
 - o ACLF Grade 1, 2 or 3a defined per the CLIF-C OF score system OR
 - o single hepatic organ failure for serum bilirubin > 20 mg/dL (342 µmol/L) at screening and randomization, OR
 - \circ AKI-stage 1b (sCr > 1.5 mg/dL or 134 μ mol/L)¹².
- Where a subject has received corticosteroids for alcohol hepatitis and is deemed unresponsive to steroids after 7 days of treatment (lack of response defined as Lille score¹³ of > 0.45 or steroids stopped before 7 days due to any complication such as infection). This refers to the first course of corticosteorid therapy. Further courses of corticosteroids during the course of illness must not be used to determine steroid responsiveness.

5.3.2. Exclusion criteria

- Co-infection with HIV and AIDS defining illness¹⁴
- Subjects with acute or sub-acute liver failure without underlying cirrhosis.
- Subjects with severe thrombocytopaenia, as defined by the platelet count of <40,000/mm³ (at screening) or rapid reduction in platelet count (> 50% reduction) in the previous 24 hrs prior to randomisation (day 0)
- Subjects with International Normalised Ratio (INR) > 3.
- ACLF 3b patients, i.e. ACLF with more than 3 organ failures.
- Subjects with cirrhosis who develop decompensation at any time in the post-operative period following partial hepatectomy or major liver surgery.
- Subjects with uncontrolled infection. Patients may be entered into the study provided antimicrobials have been administered for at least 48 hours with an appropriate response observed prior to randomization.
- Subjects with respiratory organ failure (as per CLIF-C OF scoring: PaO₂/FiO₂≤ 200 mmHg or 27 kPa or SaO₂/FiO₂ ≤ 214).
- Subjects with haemodynamic instability:
 - o i) persistent hypotension (mean arterial pressure < 65 mmHg) with evidence of tissue hypoperfusion, not responsive to volume resuscitation and/or low dose vasopressor support;

¹² See appendix 2 for further definitions and justification.

¹³ See appendix 2 for further definitions.

¹⁴ A patient can be HIV +ve as long as they are clinically stable and not presenting with any AIDS defining illness i.e. a CD4+ T-cell count below 200 cells/uL

a CD4+ T-cell percentage of total lymphocytes of less than 15%

or one of the defining illnesses such as PCP, Kaposi's sarcoma, CMV, Candidiasis etc

Clinical Investigation Plan CIP YAQ-002	Version: 7.0 10 October 2019
---	------------------------------

- ii) a norepinephrine dose of > 0.2 μg/kg/min, or a second pressor (terlipressin for variceal haemorrhage and/or hepato-renal syndrome does not count as pressor, unless it is specifically used to treat systemic hypotension) at screening or randomization. Patients can be reconsidered for study inclusion after at least a 24 hour period of norepinephrine requirement < 0.2 μg/kg/min.
- Subjects not considered appropriate for full active treatment including organ support or those with a Do Not Attempt Cardio-Pulmonary Resuscitation order (DNACPR). Subjects with active or history of non hepatic malignancy unless adequately treated or in complete remission for five or more years.
- Patients with HCC outside Milan criteria.
- Significant systemic or major illness other than liver disease, including coronary artery disease, cerebrovascular disease, pulmonary disease, renal failure, serious psychiatric disease, that, in the opinion of the Investigator would preclude the subject from participating in and completing the study.
- Any subject who has received any investigational drug or device within 30 days of dosing or who is scheduled to receive another investigational drug or device in the course of the study; concomitant observational studies are allowed.
- Evidence of uncontrolled seizures.
- Subjects diagnosed with Creutzfeldt-Jakob disease.
- In females: known pregnancy or lactating.
- Subjects weighing less than 30 kg (as per contra-indication of oXiris and septeX)
- Where subjects present with a known allergy to heparin or have type II thrombocytopaenia caused by heparin (HIT syndrome type II).
- In the opinion of the investigator, it is unsafe for the patient to be considered for the study.

5.3.3. Criteria and procedures for subject withdrawal or discontinuation

Other than those required for liver dialysis, no additional Investigation or interventions are expected over and above the routine SOC, which the patient will continue to receive. It is anticipated, therefore, that all subjects will continue to be highly compliant with the CIP study procedures. Non-compliance with the CIP study procedures will be documented by the investigator and reported to the Sponsor as agreed. Persistent non-compliance may lead to be withdrawn of the patient from the study.

The participant may, however, voluntarily choose to withdraw from the study at any time for any reason. This will not in any way affect their routine care. If the participant loses capacity during the study, the legal representative (if appointed) also has the right to withdraw the participant in this instance, acting on the presumed wishes of the participant.

The investigator also has the right to withdraw a patient at any time due to failure to follow CIP, administrative, safety or other reason. Stopping rules (for the study and for the DIALIVE treatment) have been developed as follows:

- A) Rules for discontinuing DIALIVE therapy during a treatment session, based on safety grounds
 - a. Persistent shock (MAP < 65mmHg or < 90% pre-treatment value, whichever is higher) for > 2 hrs with features of tissue hypoperfusion, unresposive to volume resuscitation and/or low dose noradrenaline (0.1µg/kg/min). Treatment can be restarted once haemodynamic stability is restored.
 - b. Deteriorating respiratory failure as defined by worsening PaO₂/FiO₂ to < 200 mmHg (27 kPa) and SaO₂/FiO₂ to < 214. Treatment can be recommenced following a 12 hour recovery period.
 - c. Disseminated Intravascular Coagulation (DIC). Thrombocytopenia alone (to below exclusion criterion threshold) without evidence of DIC is not a stopping rule. Platelet treatment should be considered in this case.
 - d. Progression to more than 3 organ failures

Clinical Investigation Plan CIP YAQ-002 Version: 7.0 10 October 20	19
--	----

- e. In the opinion of the PI, the treatment is unsafe to continue
- B) Study stopping rules for patients randomized to either the SOC or the DIALIVE arm
 - a. Withdrawal of patient consent by the patient (or if applicable the appointed respresentative, where the patient were to lose capacity during this process).
 - b. Following review of safety data by the DSMB if they wish to stop the study on safety grounds

The reasons for screen failure or withdrawal shall be documented in the eCRFs and in the patient notes. If a withdrawal is on the grounds of safety the Investigator will seek permission from the patient, or legal representative as appropriate, to follow up his/her status outside of the Investigation, but at least until resolution or full clarification of the adverse event.

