Primary End Point	To evaluate the safety of the DIALIVE in patients with Acute on chronic liver failure (ACLF)	The percentage of subjects who experience at least one (1) serious adverse event (SAE) between study Day 1 and Day 10; especially the incidence rate of SAE in both arms of the study at Day 1 and Day 10. The percentage of subjects who discontinued DIALIVE due to a serious adverse device event (SADE) between Day 1 (first day of treatment) and Day 10 (DIALIVE arm only).
Secondary End Point(s)	To evaluate the impact of biochemical performance outlined hereunder towards clinical benefit for patients receiving DIALIVE treatment plus Standard of Care vs Standard of Care alone	 Mortality: 28-days and 3 months Change in ACLF Grade Change in CLIF-ACLF score Improvement in individual organ function: brain (HE), kidney (serum creatinine), CVS (mean arterial pressure), pulmonary (P/F ratio or S/F if arterial blood gas info is not available), liver (serum bilirubin) and coagulation (INR and platelet levels). Status of ICU and Hospital Discharge (including discharge to a hospice for palliative care). Lengths of stay in ICU and hospital at D28 and D90. ICU and hospital re-admissions with another episode of ACLF up to 90 days post randomization.

Clinical Investigation Plan	CIP YAQ-002	Version: 7.0 10 October 2019
-----------------------------	-------------	------------------------------

Secondary end	Objectives	Outcomes Measures
Point(s)	To evaluate the performance of the DIALIVE in patients with ACLF	 Change in Plasma endotoxin level (endotoxin activity and endotoxin concentration) between; Study D1,D3, D5 and D10 across SOC arm
		2. Study D1, D3, D5 and D10 across DIALIVE arm
		Start and end of a treatment session with
		DIALIVE on D1, D2 and D3 4. Study D1, D3, D5 and D10 between SOC and DIALIVE arms for patients with the same grade of ACLF at the time of inclusion in the study
		Target-Value (TV): 40% reduction; Acceptable-Value (AV): 20% reduction Change in Albumin function (Human non- mercapt albumin -2 (HNA-2) / Human marcapt albumin (HMA) ratio:
		5. Study D1, D3, D5 and D10 across SOC arm6. Study D1, D3, D5 and D10 across DIALIVE
		arm 7. Start and end of a treatment session with DIALIVE on D1, D2 and D3.
		8. Study D1, D5 and D10 between SOC and DIALIVE arms for patients presenting with the same grades of ACLF
		TV: 40% reduction; AV: 20% reduction

Clinical Investigation Plan CIP YAQ-002 Version: 7.0 10 0	October 2019
---	--------------

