Commencement of DIALIVE treatment session i.e. connection of patient to the Prismaflex machine = time point 0, can occur at any time before the end of study Day 1 subject to availability of all relevant information required for treatment to commence. All blood samples should be measured from this time point. Any pre samples required should be taken just before connection.

Nuts and bolts of DIALIVE Treatment: a ready reference

-Before starting treatment

The patient to be moved to an intensive care unit or similar once randomised to DIALIVE. Appropriate monitoring needs to be instituted including the following:

- Insertion of an arterial line for continuous invasive blood pressure monitoring and blood sampling
- Insertion of a vascular catheter for DIALIVE treatment
- Insertion of a central venous catheter for prompt treatment with vasopressors if required (Lines should be inserted under USS guidance. Correction of clotting abnormalities, if any, should follow local protocols. The line positions should be confirmed through appropriate means; e.g. CXR for neck lines).

 * NB: Majority of ACLF grade 3 patients are likely to be already in the ICU with the above monitoring in situ.

Additional tests (Baseline samples for FBC, U/E, LFT, coagulation, septic screen will already have been collected to check eligibility) prior to commencing DIALIVE therapy will be done:

Arterial blood gas analysis

- Haemolysis screen (FBC including reticulocyte count, blood film, unconjugated and conjugated bilirubin, LDH, haptoglobin, urinary free haemoglobin) – to be performed only on D1, before and after therapy
- DIC screen, if clinically indicated
- And, Endotoxin Activity Assay (EAA) analysis (start of day 1, 2 and 3)
- Blood to be collected as part of biobank samples.(start of day 1, 2 and 3)

Fluid pre-loading of up to 500mls over 1-2 hours is implemented, the volume and speed of fluid therapy to be determined on a clinical basis, and the choice of fluid would preferably be albumin (4.5 or 5% solution as per local availability).

- during dialysis session

- Anticoagulation with unfractionated heparin and/or prostacycline analogues (the dose as per local protocols)
- Blood flow rates on DIALIVE device to be started at 50 mls/min and increased gradually over 1-2 hours to up
 to a maximum of 250 mls/min

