5.1.3 Secondary End Points

To evaluate the performance of the DIALIVE in patients with ACLF. This is measured by;

Change in Plasma endotoxin level (endotoxin activity and concentration) between;

D1, D3, D5 and D10 across SOC arm $\,$

D1, D3, D5 and D10 across DIALIVE arm

_

¹⁰ In case a patient's treatment is discontinued, the follow up period will remain 28 days from the moment of randomization.

Clinical Investigation Plan	CIP YAQ-002	Version: 7.0 10 October 2019
-----------------------------	-------------	------------------------------

Start and end of a treatment session (on D1, D2 and D3) with DIALIVE D1,D3, D5 and D10 between SOC and DIALIVE arms for patients presenting with the same grades of ACLF (i.e. Grade 1 ALCF compared with Grade 1 ACLF)

Target-Value (TV): 40% reduction; Acceptable-Value (AV): 20% reduction at end of treatment cycle.

• Change in Albumin function (Human non-mercapt albumin -2 (HNA-2) / Human marcapt albumin (HMA) ratio:

D1, D3, D5 and D10 across SOC arm
D1,D3, D5 and D10 across DIALIVE arm
Start and end of a treatment session (on D1, D2, D3) with DIALIVE
D1,D3, D5 and D10 between SOC and DIALIVE arms for patients presenting with the same grades of ACLF (i.e. Grade 1 ALCF compared with Grade 1 ACLF)

TV: 40% reduction; AV: 20% reduction at end of treatment cycle.

- Mortality: 28-days and 90 days
- Change in ACLF Grade
- Change in CLIF-ACLF score
- Improvement in individual organ function: Brain (HE), Kidney (creatinine), CVS (mean arterial pressure), Pulmonary (P/F ratio, or S/F if patient is not intubated), Liver (serum bilirubin) and coagulation (INR and platelets).
- Status at ICU and Hospital Discharge (including discharge to a hospice for palliative care).
- Lengths of stay in ICU and Hospital at D28 and D90
- ICU and Hospital re-admissions with another episode of ACLF up to 3 months after randomisation.

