Appendix 1b:Chronic Liver Failure Consortium (CLIF-C) Scoring Systems

CLIF-C Organ Failure (CLIF-C OF) Scoring System

Organ System	Score = 1	Score = 2	Score = 3
Liver (mg/dl)	Bilirubin < 6	6 ≤ Bilirubin ≤ 12	Bilirubin >12
Kidney (mg/dl)	Creatinine <2	Creatinine ≥2 <3.5	Creatinine ≥3.5 or renal replacement
Brain (West-Haven)	Grade 0	Grade 1-2	Grade 3-4
Coagulation	INR < 2.0	2.0 ≤ INR < 2.5	INR ≥ 2.5
Circulation	MAP ≥70 mm/Hg	MAP <70 mm/Hg	MAP < 65 mmHg; Vasopressors
Respiratory: PaO2/FiO2 or SpO2/FiO2	>300 >357	≤300 - > 200 >214- ≤357	≤200 ≤214

The shaded areas represent 'Organ Failures'

From: Jalan R, Saliba F, Pavesi M, Amoros A, Moreau R, Gines P, et al. Development and validation of a prognostic score to predict mortality in patients with acute-on-chronic liver failure. Journal of Hepatology 2014; 61: 1038–1047

CLIF-C Acute Decompensation (CLIF-C AD) Formula

10*0.03*Age + 0.66*Ln Creatinine + 1.71*Ln INR + 0.88*Ln WBC +-0.05*Sodium + 8

From: Jalan R, Pavesi M, Saliba F, Amoros A, Fernandez J, Holland-Fischer P, et al. The CLIF Consortium Acute Decompensation score (CLIF-C ADs) for prognosis of hospitalised cirrhotic patients without acute-onchronic liver failure. Journal of Hepatology 2015; 62: 831–840

CLIF-C Acute-on-Chronic Liver Failure (CLIF-C ACLF) Formula

10*[0.33*CLIF-OFs + 0.04*Age + 0.63*Ln WCC - 2]

From: Jalan R, Saliba F, Pavesi M, Amoros A, Moreau R, Gines P, et al. Development and validation of a prognostic score to predict mortality in patients with acute-on-chronic liver failure. Journal of Hepatology 2014: 61: 1038–1047

Clinical Investigation Plan CIP YAQ-002 Version: 7.0 10 0	October 2019
---	--------------

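### Respiratory stopping rule 5.3.3 A(b) requires both oxygenation ratios to fall, so a treated patient with P/F below 200 can miss the objective stop

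*Protocol*

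**What the plan says.** Section 5.3.3 A lists the safety grounds for discontinuing DIALIVE during a session. Item (b) covers deteriorating respiratory failure and joins its two thresholds with a conjunction: P/F must fall "to < 200 mmHg (27 kPa) and" S/F must fall below 214. Treatment may resume after 12 hours of recovery.

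Elsewhere the same cut-offs are alternatives:

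- The exclusion criterion in 5.3.2 (and in the synopsis) bars respiratory failure by CLIF-C OF scoring, at P/F of "200 mmHg or 27 kPa or" the S/F limit.
- Appendix 1b labels the scoring row "Respiratory: PaO2/FiO2 or SpO2/FiO2".
- The pulmonary endpoint uses S/F only in place of P/F: "P/F ratio or S/F if arterial blood gas info is not available" in the synopsis and "P/F ratio, or S/F if patient is not intubated" in 5.1.3.

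Two other items in the same list could apply to a patient whose lungs are failing. These are A(d), "Progression to more than 3 organ failures", and A(e), "In the opinion of the PI, the treatment is unsafe to continue".

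Section 2.2 requires, before treatment, "Insertion of an arterial line for continuous invasive blood pressure monitoring and blood sampling", and blood gases every two hours during a session.

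**The concern.** A(b) is the only place in the protocol where both ratios must be abnormal at once. A patient whose P/F has dropped below 200 would be in respiratory failure under 5.3.2 and Appendix 1b. That patient would not meet A(b) until the saturation ratio had also fallen. Saturation falls late when PaO2 falls, so the delay can be material at moderate FiO2.

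This is one of the few numerical stops in a first-in-man device study that section 5.5 rates as high risk, and section 5.3.4 expects about three patients per centre. Sites will have little experience of their own to fall back on, so the written rule should have one meaning. As it stands, one site may stop on P/F alone while another waits for both ratios.

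**Working it through.** The protocol gives no figure to reproduce. The check is whether the combination that escapes A(b) can occur, and whether another stop catches it.

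**Inputs.** The cut-offs of 200 mmHg for P/F and 214 for S/F are from 5.3.3 A(b), 5.3.2 and Appendix 1b. The gas values in the examples are assumed for illustration.

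**Step 1: when can P/F be below 200 with S/F at 214 or more?**

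- P/F < 200 requires PaO2 < 200 × FiO2.
- S/F ≥ 214 requires SaO2 (%) ≥ 214 × FiO2. SaO2 cannot exceed 100%, so FiO2 can be at most 100/214 = 0.467.

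| FiO2 | PaO2 at P/F 200 (mmHg) | SaO2 at S/F 214 (%) | Highest possible S/F |
|---|---|---|---|
| 0.40 | 80 | 85.6 | 250 |
| 0.45 | 90 | 96.3 | 222.2 |
| 0.50 | 100 | not attainable (107.0) | 200 |

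At FiO2 0.40 the P/F limb is met once PaO2 is under 80 mmHg, but the conjunction also waits for SaO2 under 85.6%.

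**Step 2: examples at FiO2 0.40.**

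| PaO2 (mmHg) | SaO2 (%) | P/F | S/F | 5.3.2 | A(b) as written | A(b) reworded |
|---|---|---|---|---|---|---|
| 78 | 95 | 78/0.40 = 195 | 95/0.40 = 237.5 | failure | no stop | stop |
| 64 | 88 | 64/0.40 = 160 | 88/0.40 = 220 | failure | no stop | stop |

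**Step 3: how long might the delay be?** This step assumes a standard oxygen dissociation curve, which is not in the protocol: SaO2 = 100/(23400/(p³ + 150p) + 1), where p is PaO2 in mmHg.

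| FiO2 | S/F when P/F is exactly 200 | PaO2 at which S/F reaches 214 (mmHg) | P/F at that point |
|---|---|---|---|
| 0.40 | 239 | about 51 | about 127 |
| 0.45 | 215 | about 84 | about 187 |
| 0.50 | 195 | already below 214 | no delay |

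On this assumption the delay is large at FiO2 0.40, small at 0.45 and absent at 0.50.

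**Step 4: do the other stops close the gap?** Respiratory failure is excluded at entry, so during treatment it is a new failure. It takes a patient with one other failure to two, or with two others to three, and neither exceeds three. A(d) fires only when three other failures are present. A(e) can apply to anyone but is a judgement.

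**Step 5: would a bare 'or' be enough?** No. At FiO2 0.50 and PaO2 120 mmHg, P/F is 240 and S/F is at most 200. A simple 'or' would stop this patient whatever the saturation. An S/F limb that applies only when there is no arterial gas avoids this.

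**The case against.** The best reply is that the conjunction is loose drafting. A(b) addresses a condition the protocol has already defined with alternative thresholds, and the sentence can be read as giving each ratio its own limit. That is probably what was meant. But the literal text says otherwise, nothing in the protocol corrects it, and a safety stop should not depend on a charitable reading.

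A second reply is that a stop need not mirror entry. A(a) departs from the haemodynamic entry criterion without explanation, so the absence of a reason in A(b) does not prove an error. This is fair. The point rests on the outcome of the literal rule, not on a lack of symmetry.

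A third reply is that these patients are closely watched, in intensive or high-dependency care with an arterial line, two-hourly gases and senior supervision in the first hours. The investigator can also withdraw a patient at any time. This stands, and it limits the harm.

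A reader might infer more than the documents support:

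- **That patients are left unprotected.** A(e) and the monitoring contradict this.
- **That A(b) also fails at higher FiO2.** Above 0.467 the S/F limb is always met, so A(b) reduces to P/F < 200 and works. Any mismatch there comes from the literal 'or' in the entry criterion.
- **That entry should be rewritten to match.** Letting P/F govern at entry would admit patients now excluded, such as one with FiO2 0.50 and P/F 240. That loosens a safety exclusion in a first-in-man study, and the stop can be repaired without it.
- **That the results are compromised.** Under section 6 the main analysis uses the safety population, and evaluable patients enter only a sensitivity analysis. Any effect through who completes a cycle is minor.

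The differences between strict and non-strict inequality signs, and between the two endpoint conditions for using S/F, are side matters and carry no weight here.

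**Conclusion.** The point holds as a defect in the wording of A(b). Taken literally, the rule misses patients with P/F below 200 and S/F of 214 or more, a combination possible only at FiO2 below 0.467. A(d) catches such a patient only when three other organs have failed, and A(e) is discretionary. The consequence is an objective stop that may be applied inconsistently between sites.

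The 0.467 limit and the two examples follow from the protocol's own cut-offs by arithmetic, given the assumed gas values. The P/F values at which the literal rule would eventually fire rest on the assumed dissociation curve, and the verdict does not depend on them. The protocol gives no frequency for this combination in treated patients, so the number affected cannot be estimated. The correction is worth making because it is cheap and concerns safety, not because harm has been shown.

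**What to change.** Reword A(b) only, to: *worsening PaO2/FiO2 to ≤ 200 mmHg (27 kPa), or SaO2/FiO2 to ≤ 214 if no arterial blood gas is available*. Treated patients have an arterial line and two-hourly gases, so P/F will normally govern. Tell sites of the change, and leave the exclusion criterion in the synopsis and 5.3.2 as it is.

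The cost is one clause and a site notice, plus some sessions paused for 12 hours that the literal rule would have let continue. Section 2.2 counts a cumulative break of more than 4 hours within a session as a session failure, which restarts the cycle, and a second failed session within the 10-day window excludes the patient. Some extra session failures, and possibly some replaced patients, should be expected.
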